NCT04088097

Cognitive Behavioral Therapy for Adolescent Binge Eating and Loss of Control Eating

Document date: 3/13/2024

HRP-503B – BIOMEDICAL RESEARCH PROTOCOL
(2017-1)

Protocol Title: Development and Initial Efficacy Testing of a Cognitive-Behavioral Intervention to Treat Adolescent Binge Eating

Principal Investigator: [name]., Assistant Professor in Psychiatry

Version Date: Version 9 (2/28/2024)

(If applicable) Clinicaltrials.gov Registration #: NCT04088097

SECTION I: RESEARCH PLAN

1. **Statement of Purpose:** State the scientific aim(s) of the study, or the hypotheses to be tested.

The overall aim of the study is:

1. To develop a cognitive-behavioral therapy (CBT) that treats adolescent binge/loss-of-control (LOC) eating and test whether this new CBT for adolescent binge/LOC eating is superior to an active control group.

Hypothesis 1: Adolescents randomized to CBT will have a greater reduction in binge/LOC eating (episode frequency) than adolescents in the active control group.

Hypothesis 2: Adolescents randomized to CBT will have a greater reduction in weight (BMI z-score using measured height and weight) than adolescents in the active control group.

2. **Probable Duration of Project:** State the expected duration of the project, including all follow-up and data analysis activities.

Development and evaluation of the treatment is expected to occur over 6 years (including follow-up and data analysis).

3. **Background:** Describe the background information that led to the plan for this project. Provide references to support the expectation of obtaining useful scientific data.

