Adolescents will be recruited using flyers in the community, primary care and other medical offices, and schools (104, 105). Our research facilities are local to these community spaces and should present minimal location-based barriers. Adolescents will have excess weight and regular binge/LOC eating without any contraindications (see inclusion/exclusion criteria) to be eligible for treatment.

7. **Subject classification:** Check off all classifications of subjects that will be specifically recruited for enrollment in the research project. Will subjects who may require additional safeguards or other considerations be enrolled in the study? If so, identify the population of subjects requiring special safeguards and provide a justification for their involvement.

 Children	 Healthy	 Fetal material, placenta, or dead fetus
 Non-English Speaking	 Prisoners	 Economically disadvantaged persons
 Decisionally Impaired	 Employees	 Pregnant women and/or fetuses
 Yale Students	 Females of childbearing potential	

NOTE: Is this research proposal designed to enroll children who are wards of the state as potential subjects?

Yes No

8. **Inclusion/Exclusion Criteria:** What are the criteria used to determine subject inclusion or exclusion?

Inclusion Criteria: To be included, adolescents must:

1. Be in the age range ≥ 12 years old and ≤ 17 years old;
2. Have a BMI that places them above the 85th percentile based on their age and sex;
3. Report 2 episodes of binge/LOC eating (feeling a loss of control while eating) per month for the past 3 months;
4. Be otherwise-healthy youth (i.e., no uncontrolled or serious medical conditions);
5. Read, comprehend, and write English at a sufficient level to complete study-related materials;

6. Provide a signed and dated written assent prior to study participation;
7. Provide a signed and dated written consent from one parent prior to study participant; and
8. Be available for participation in the study for 7 months.

Exclusion Criteria: Prospective participants will be excluded if the adolescent:

1. Has a medical or psychiatric condition that would require hospitalization or intensive care (e.g., neurological disorder, psychotic disorders, suicidality);

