Study participant safety will be monitored by the study team and reported to the PI at all visits and referrals will be provided if warranted and/or requested. If a study participant experiences any psychiatric symptoms or distress (e.g., depressive symptoms or suicidality) at any stage of study participation they will receive short-term treatment and support from the study treatment team (which includes psychologists) and will be connected to a local emergency department and their physician or therapist for ongoing care.

Other Potential Issues Relating to Stopping Rules for the Pilot RCT Include:

- 1) **New Information:** It is unlikely that any new information would become available during this trial that would necessitate stopping the trial. If new data become available, these will be evaluated.
- 2) **Limits of Assumptions:** It is possible that baseline differences between the treatment conditions, excessive attrition, and/or missing data could limit the value of data analysis. Baseline differences across treatment groups, if present, will be evaluated twice yearly and considered in relation to potential effects on the power to detect differences in the primary outcomes. If these effects were to develop and be sizeable, alterations to the randomization schedule would be considered. Any plans to alter the randomization scheme would be communicated to the NIH.
- 3) **Limits of Rules:** There are other situations that could occur that might warrant stopping the trial and/or including a section on the safety report entitled “Other situations that have occurred since the last safety report that warrant discussion” to allow for communication of concerns.

13. **Statistical Considerations:** Describe the statistical analyses that support the study design.

DATA ANALYSIS AND AIMS

Baseline demographic and clinical characteristics will be compared between treatment and control groups using chi-square tests for categorical variables (e.g., sex) and ANOVAs or Kruskal-Wallis tests for continuous variables (e.g., BMI z-score). Continuous variables will be examined for adherence to normality using probability plots and Kolmogorov-Smirnov tests. If normality is not satisfied and transformations do not achieve acceptable normality, alternative strategies (e.g., nonparametric) will be considered. Dropouts and completers will also be compared. Analyses will be intent-to-treat. Outcomes will be tested at the $\alpha=0.05$ threshold.

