Overall analysis strategy. Descriptive statistics will quantify change and mixed-effects models (106, 107) will compare treatments through post; 3-month follow-up will be exploratory. These models allow for different numbers of observations per participant, use all available data on each participant, account for clustered data observations, and are unaffected by data missing at random. A further advantage is the capacity to test and account for individual-difference contributions to treatment outcomes (108). This strategy provides flexibility in modeling the correlation structure of the data. In models for each outcome, we will include fixed effects of time and treatment and their interaction, and random subject-level effects. Because we cannot *a priori* predict the shape of the response over time, we will first treat time as categorical and then test for polynomial trends. We will consider different error structures (e.g., compound symmetry, autoregressive) and select the best-fitting structure based on information criteria. Data on all participants enrolled in the study will be used in mixed models. We will compare dropout patterns and if there are concerns of informative dropout and/or informative intermittent missing data, we will use pattern mixture models to perform sensitivity analyses to main analyses.

Primary Aims.

Primary Aim 1 is to **test** the efficacy of adolescent CBT relative to the active control condition at post-treatment on clinical outcomes, including: (a) reduction in binge/LOC eating frequency (evaluated by the QEWP), and (b) reduction in weight (evaluated by BMI z-score). Significant time-by-treatment effects with significantly less adolescent binge/LOC eating and significantly reduced weight in adolescent CBT relative to the control condition will be considered supportive of these aims. Parallel analyses will also assess binge/LOC frequency reduction using the EDE; because this interview is only administered at baseline and post, this analysis will, by definition, occur among completers. Adolescent CBT is hypothesized to yield reduced binge/LOC eating frequency and weight reduction (i.e., weight loss or less excess weight gain) compared to the control group.

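### The plan fixes no distribution, link or baseline adjustment for the primary binge/LOC episode frequency, so the data choose the scale of the primary effect

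*Combined protocol and SAP*

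**What the plan says.** Section I, 1 (Statement of Purpose), Hypothesis 1: "Adolescents randomized to CBT will have a greater reduction in binge/LOC eating (episode frequency) than adolescents in the active control group". Section I, 13, Primary Aims, makes outcome (a) the "reduction in binge/LOC eating frequency (evaluated by the QEWP"; how the QEWP is scored, and over what recall window, is not stated. Table 2 schedules the QEWP at baseline, Months 1 to 3, post and follow-up, which gives five visits through post.

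Entry requires adolescents to "Report 2 episodes of binge/LOC eating (feeling a loss of control while eating) per month for the past 3 months" (Section I, 8).

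On distribution, the opening paragraph of Section I, 13 says: "Continuous variables will be examined for adherence to normality using probability plots and Kolmogorov-Smirnov tests". It continues: "If normality is not satisfied and transformations do not achieve acceptable normality, alternative strategies (e.g., nonparametric) will be considered".

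On the efficacy model, the paragraph on overall analysis strategy says "mixed-effects models (106, 107) will compare treatments through post; 3-month follow-up will be exploratory", and "In models for each outcome, we will include fixed effects of time and treatment and their interaction, and random subject-level effects". The error structure is to be picked by information criteria. No Poisson, negative binomial, ordinal or other non-Gaussian model is named, and the baseline value of the outcome is not named as a covariate. The power paragraph works only in standardised effects (d), and gives as a purpose of the trial the supply of effect sizes for definitive studies.

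**The concern.** An episode frequency with a low entry threshold, in a trial that aims to reduce it, will probably be right-skewed with a fair share of zeros at post. The natural effect is a ratio of rates. The written route instead checks normality, then transforms, then looks for something else. A raw mean difference, a difference in log counts and a rank statistic answer different questions, and a d on one scale does not carry over to another. If the data select among them, the effect size passed to the next grant is not known in advance.

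Two features add weight. The trial is unblinded, and the investigator reviews interim analyses twice yearly (Section I, 12), so an open choice of scale is weakly protected. Also, with baseline treated only as a level of time, the time-by-treatment contrast at post is a difference of changes. For equal variances and correlation ρ between baseline and post, its variance relative to a baseline-adjusted comparison is 2σ²(1−ρ) / σ²(1−ρ²) = 2/(1+ρ), which exceeds 1 whenever ρ < 1. For raw counts that fall over time the penalty is larger, because the baseline values carry the greater variance.

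**Working it through.** **1. The plan's own figure.** Inputs from the power paragraph: two-sided α = 0.05, 25 per arm, or 20 per arm after 20% dropout. Normal approximation: power = Φ(d√(n/2) − 1.96) between groups.
- n = 25, d = 0.8: Φ(2.83 − 1.96) = 80.7%; exact t, 79.2%.
- n = 20, d = 0.9: Φ(2.85 − 1.96) = 81.2%; exact t, 79.2%.
- Within group, exact t: d' = 0.58 at n = 25 gives 79.5%; d' = 0.66 at n = 20 gives 80.0%.

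The stated 80% reproduces, but says nothing about a count.

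**2. Effect of scale, baseline handled alike.** All inputs except n are assumptions. Five visits, gamma-Poisson counts with a log-normal subject effect, baseline count at least 2, complete data, 500 runs per setting (about ±4 points). Each model has time, treatment, interaction and a subject effect, with baseline as a visit. The test is the post-versus-baseline contrast. Power is size-adjusted, using null runs of the same setting.

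| Baseline mean; control post mean | SD of log subject effect; dispersion | Rate ratio | Zeros at post | K-S rejects | Neg. binomial | Raw | Log(1+count) | Ranks |
|---|---|---|---|---|---|---|---|---|
| 8; 6 | 0.7; 0.4 | 0.4 | 16% | 61% | 79.6% | 43.0% | 71.0% | 70.0% |
| 8; 6 | 0.7; 0.4 | 0.5 | 14% | 62% | 58.6% | 31.2% | 52.4% | 53.6% |
| 8; 6 | 1.0; 0.5 | 0.4 | 21% | 83% | 76.2% | 38.0% | 65.8% | 63.0% |
| 12; 8 | 1.0; 0.3 | 0.5 | 13% | 78% | 70.2% | 27.0% | 63.6% | 57.0% |
| 6; 4 | 0.5; 0.6 | 0.4 | 25% | 61% | 76.0% | 31.6% | 64.0% | 60.0% |

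Loss against the count model:
- log: 6 points (58.6 − 52.4) to 12 (76.0 − 64.0)
- ranks: 5 (58.6 − 53.6) to 16 (76.0 − 60.0)
- raw: 27 (58.6 − 31.2) to 44 (76.0 − 31.6)

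The raw loss applies only where raw counts pass the check, here 17% to 39% of trials. Before size adjustment, the count model's type I error was 4.8% to 7.8%. The mean raw d at post was 0.49 to 0.74 across these rate ratios, so d does not identify a rate reduction.

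**3. Separating baseline adjustment from scale.** Two visits, 25 per arm, assumed gamma-Poisson counts, 400 runs. The same pretest path was run without and with baseline adjustment, then compared with a baseline-adjusted negative binomial model.

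| Setting | Path, unadjusted | Same path, adjusted | Neg. binomial, adjusted | Total gap | From baseline adjustment | Remainder |
|---|---|---|---|---|---|---|
| Rate ratio 0.5, 16% zeros | 43% | 59% | 62% | 19 | 16 | 3 |
| Rate ratio 0.4, 18% zeros | 63% | 81% | 85% | 22 | 18 | 4 |
| Rate ratio 0.4, 39% zeros | 19% | 55% | 66% | 47 | 36 | 11 |

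Baseline adjustment supplies 16/19 = 84%, 18/22 = 82% and 36/47 = 77% of the gap. The unadjusted path ends in a Mann-Whitney test on change, which the plan does not name, so this table serves attribution only. A further two-visit check (2,000 runs) agrees: a raw change score lost 37 to 54 points, but a raw-count analysis adjusted for baseline lost 3 to 6.

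**4. The plan's path over five visits.** The time-by-treatment mixed model with the scale chosen by the check was set against a baseline-adjusted negative binomial analysis at post (400 runs per setting, complete data).
- Raw counts passed the check in 10% to 40% of trials.
- Power was 18% to 45% for the path and 44% to 80% for the count model, a gap of about 25 to 38 points.
- A baseline-adjusted log(1+count) analysis alone reached 36% to 77%.
- The count model ran at about 7% under the null, so part of its nominal advantage is inflated size.

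**The case against.** The strongest reply is that the text does not commit to a poor analysis. The normality sentence speaks of continuous variables, follows directly on the baseline comparisons, and uses probability plots as well as a test. Its last step is open: "alternative strategies (e.g., nonparametric) will be considered". The strategy paragraph says mixed-effects models without saying Gaussian. All of this stands. A reader might infer that the plan excludes a count model, or that it would abandon the mixed model, and with it the handling of missing data, for a rank test. The documents do not support either inference: a count model is unspecified, and the mixed model is said to apply to every outcome.

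That reply does not remove the gap. The baseline sentence already carries its own nonparametric option, and the same paragraph goes on to intent-to-treat and the significance level for outcomes, so applying the rule to outcomes is reasonable. If it does not apply, the primary outcome has no distributional rule at all. Choosing among compound symmetry and autoregressive errors is also usual Gaussian-model language.

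The second reply concerns size. A reader might infer that the normality check itself costs large amounts of power, up to the 47 points in step 3. It does not: most of that gap is baseline handling. Nor can any fixed loss be stated, since the only anchor in the documents is the entry threshold. Finally, the plan calls the trial a pilot with limited power. That tempers the power argument but not the need for one defined effect measure.

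**Conclusion.** The point holds as a gap in pre-specification. The scale of the primary effect is left to the data, and no baseline adjustment is named. That the normality rule governs this outcome is a reasonable reading, not an explicit statement.

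The direction of the power loss is consistent across the checks; its size is not a property of the documents. Under the assumed counts, the unadjusted time-by-treatment path falls about 25 to 38 points short of a baseline-adjusted count model. Most of such a shortfall is attributable to baseline adjustment. Scale and pretest alone account for roughly 3 (step 3) to 16 points (step 2, ranks), and more only where raw counts pass the check. These figures rest on gamma-Poisson data, complete follow-up and 400 to 500 runs per setting; the smallest differences are within simulation error. If the QEWP yields categories rather than a count, the figures do not apply, but the need to name a model does.

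**What to change.** Before outcome data are examined:
- State the QEWP scoring and recall window for binge/LOC frequency.
- Exempt this outcome from the normality check and name one baseline-adjusted primary analysis.
- If the score is a count, use a log-link negative binomial mixed model of the post-baseline visits through post, with time, treatment, their interaction, log baseline count as covariate and a random subject effect. Baseline should not also be an outcome visit.
- Use a permutation or other small-sample reference, since nominal type I error reached about 7% to 8% at this size. Confirm the chosen reference by simulation, because the checks above did not test it for the mixed model.
- Report the CBT:control rate ratio at post with a 95% confidence interval.
- Name the fallback: a baseline-adjusted mixed model on log(1+count) if the model does not converge, or an ordinal mixed model if the scoring is categorical.

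The cost is a change of wording and slightly more programming. The main risk is non-convergence with 50 participants, which the named fallback covers.

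### Primary Aim 1 is set at post-treatment, but no primary contrast is named and no baseline adjustment is listed; a 1-df baseline-adjusted CBT-control difference at post would match the aim and usually be more efficient

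*Combined protocol and SAP*

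**What the plan says.** All of this is in Section I.13, Statistical Considerations.

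- **Aim.** Primary Aim 1 tests CBT "relative to the active control condition at post-treatment on clinical outcomes", for binge/LOC frequency (QEWP) and BMI z-score.
- **Success rule.** The next sentence counts as support "Significant time-by-treatment effects with significantly less adolescent binge/LOC eating and significantly reduced weight in adolescent CBT relative to the control condition". It gives no visit and no contrast.
- **Model.** Under Overall analysis strategy, "we will include fixed effects of time and treatment and their interaction, and random subject-level effects". No baseline covariate or equal-baseline constraint is listed.
- **Time.** Because the team cannot say in advance how to "predict the shape of the response over time", "we will first treat time as categorical and then test for polynomial trends". The main comparison runs through post, and the 3-month follow-up is exploratory.
- **Error structure.** "We will consider different error structures (e.g., compound symmetry, autoregressive) and select the best-fitting structure based on information criteria".
- **EDE.** A parallel analysis uses the EDE, with completers only, "because this interview is only administered at baseline and post".
- **Non-normal outcomes.** "If normality is not satisfied and transformations do not achieve acceptable normality, alternative strategies (e.g., nonparametric) will be considered".
- **Power.** 80% for d=0.8 with 25 per arm, and for d=0.9 after 20% dropout, two-sided 0.05. The SD to which d refers is not stated.

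Section I.4 and Table 2 put both primary outcomes at baseline, Months 1, 2 and 3, and post: five occasions through post.

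**The concern.** Three tests fit the success rule: the overall time-by-treatment interaction (4 df with five categorical occasions), a polynomial trend, and a contrast at post. They answer different questions, and only the last answers an aim set at post-treatment. With 25 per arm they can also disagree, and the text leaves the choice open until the data are in.

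Two further points follow.

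- The EDE has two occasions, so its interaction is a 1-df comparison of change. If the QEWP test is the 4-df interaction, the two analyses described as parallel test different hypotheses.
- Baseline enters the model as an occasion, so a change contrast uses it at full weight. Adjusting for it, or constraining baseline means to be equal across arms, usually gives a more precise estimate of the difference at post from data the trial already collects.

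The Power Analysis paragraph says the pilot is meant to supply effect sizes for later grant applications. One named difference at post serves that purpose better than an omnibus F test.

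**Working it through.** **Inputs from the documents (Section I.13; Section I.4 and Table 2 for visits).** n=25 per arm, d=0.8; 20 per arm and d=0.9 after dropout; two-sided 0.05; five occasions through post.

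**Assumptions not in the documents.** Normal outcomes, complete data, equal variance at each visit, and d in post-score SD unless stated. Compound symmetry (CS) has correlation 0.3/0.5/0.7; AR(1) has adjacent-visit correlation 0.5/0.7/0.8. These are the two structures the plan gives as examples. The effect at post is reached either linearly or abruptly (only at post).

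**Step 1: the plan's own figure.** For an unadjusted two-sample t-test the noncentrality is d√(n/2).

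- n=25: 0.8×√12.5 = 2.83, 48 df, power 79.1%.
- n=20: 0.9×√10 = 2.85, 38 df, power 79.2%.

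The stated 80% therefore matches an unadjusted two-group comparison.

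**Step 2: the candidate tests.** Let r be the baseline-post correlation: ρ under CS, and the fourth power of the adjacent correlation under AR(1) (0.5⁴=0.06, 0.7⁴=0.24, 0.8⁴=0.41).

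- *Change to post:* noncentrality 2.83/√(2(1−r)), 48 df. At r=0.3, 2.83/√1.4 = 2.39.
- *Baseline-adjusted post difference:* variance 2(1−r²)/n × (1+1/(2n−4)), 47 df. At r=0.3, 2×0.91/25×(1+1/46) = 0.0744, so the noncentrality is 0.8/√0.0744 = 2.93.
- *Interaction:* noncentral F with 4 and 4×48=192 df. Under CS, λ = (n/2)Σ(δₖ−δ̄)²/(1−ρ), where δₖ is the arm difference at visit k. For linear divergence (0, 0.2, 0.4, 0.6, 0.8) the sum is 0.40 and λ = 5/(1−ρ). For an abrupt effect (0, 0, 0, 0, 0.8) the sum is 0.512 and λ = 6.4/(1−ρ).

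| Test (power, %) | CS 0.3/0.5/0.7 | AR(1) 0.5/0.7/0.8 |
|---|---|---|
| 4-df interaction, linear | 54/70/92 | 34/41/51 |
| 4-df interaction, abrupt | 66/82/97 | 66/86/96 |
| Change to post | 65/79/95 | 53/61/72 |
| Unadjusted post difference | 79/79/79 | 79/79/79 |
| Baseline-adjusted post difference | 82/89/97 | 78/81/85 |

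**Step 3: adjustment against change.** The variance ratio is (1−r²)/(2(1−r)) = (1+r)/2, which is 0.65/0.75/0.85 at r=0.3/0.5/0.7 and 0.95 at r=0.9. It never exceeds 1. The small-sample factor 47/46 cancels the advantage only above r = 45/47 = 0.957.

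**Step 4: units of d.** If d is in change-score SD, which the hypotheses' talk of reduction allows, change to post has 79% in every case. The adjusted contrast then has 92/89/84% under CS at 0.3/0.5/0.7 (80% at 0.9) and 96/94/90% under AR(1). The ordering against change does not depend on the units.

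**Step 5: interaction without a post effect.** Suppose the arms differ by 0.8 SD at Months 1-3 and not at all at post. The sum of squares is 3×0.64 − 5×0.48² = 0.768, so λ = 12.5×0.768/(1−ρ) = 9.6/(1−ρ). The 4-df test is then significant in 85/95/99.8% of trials under CS 0.3/0.5/0.7.

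**The case against.** - **The text already points to post.** The sentence before the success rule fixes the visit, and the rule requires a difference favouring CBT. This stands: a post contrast is a natural reading. But the rule does not name it, and the strategy paragraph leads a reader equally to the interaction or a trend.
- **The plan's own model gives an unadjusted post difference, and adjustment may add little to it.** This stands in part. Under AR(1) the adjusted contrast has 78.4/80.6/85.2% against 79.1%: a loss of 0.7 points, then gains of 1.5 and 6.1. The gain is larger under CS, but the documents give neither structure nor correlation.
- **Not presuming a response shape is deliberate, and the interaction can win.** True for an abrupt effect with decaying correlation: 86% against 81% at AR(1) 0.7, and 96% against 85% at 0.8. A stand-alone linear trend can be marginally better under CS with linear divergence (98% against 97% at 0.7). If the rule needs the interaction and a significant favourable difference together, simulation put that joint rule below the adjusted contrast in all 24 cells tried.
- **Baseline is already in the model, and covariates are not excluded.** Correct. Adjustment is a choice for efficiency, not a requirement for validity. It handles chance imbalance in the outcome's own baseline only.
- **Complete, normal data are assumed.** This stands. Repeating the formulas with 20 per arm and d=0.9 changes them by at most 0.4 points, but that does not model gradual dropout. A count simulation gave 70-92% for the adjusted test. It is illustrative only: its means, dispersion and effect are assumed and not calibrated to d=0.8. It also truncates the analysed count at entry, although eligibility is judged on the EDE and the outcome on the QEWP.

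**Conclusion.** The point holds as a worthwhile clarification. Primary Aim 1 is set at post, its rule names no contrast, and an interaction alone can be significant with no difference at post. A baseline-adjusted post difference answers the aim directly. It beat the change contrast in every case computed, though by little if the baseline-post correlation is near 0.9, as it may be for BMI z-score. There, naming the contrast is the main benefit. The gain over an unadjusted post difference is negligible under AR(1) at 0.5-0.7. All sizes rest on the assumptions listed in the working.

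Two stronger readings are tempting.

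- A reader might infer that the trial is committed to the 4-df test and therefore has power as low as 34%. The documents do not say the interaction alone is the test, and the planned analysis is valid without inflated error.
- A reader might infer that the stated 80% is wrong, or that it is a floor for the adjusted contrast. It reproduces as an unadjusted two-group comparison. No floor has been shown, least of all for the count outcome.

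**What to change.** Amend Section I.13 before analysis.

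1. For each primary outcome, name as the primary test the 1-df CBT-control difference at post, two-sided 0.05, from the categorical-time mixed model through post. Constrain baseline means to be equal across arms, or enter baseline as a covariate with a baseline-by-visit term.
2. For binge/LOC frequency, apply this on the transformed scale, or in a count model if skewness remains.
3. Use the same baseline-adjusted post contrast for the EDE.
4. Keep the overall interaction, polynomial trends and Months 1-3 contrasts as supportive.
5. State that the 80% refers to an unadjusted two-group comparison, and say whether d is in post-score or change-score SD.

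The cost is SAP wording: no new data, visits or participants. The downside is that trajectory tests lose confirmatory status. If the interaction alone would have counted as success, some power is also lost when the effect is abrupt and correlation decays quickly.
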